12.7.1.4 Repeats of AE Analyses without Censoring

In the EOT analysis the following outputs are repeated without applying any censoring rules due to subject unblinding or AV receipt:

- Overall summary of unsolicited AEs occurring through EOT Visit
- Unsolicited AEs, SAEs, unsolicited AESIs and AEs with fatal outcome, by SOC and PT occurring through EOT Visit

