5.1.3 Open-label Phase Design and Objectives

After unblinding, the trial will shift from a randomized observer-blinded to an open-label design, and the following cohorts will be defined:

Cohort A: CVnCoV-AV (See Table 4 for the Schedule of Trial Assessments and Procedures): Subjects \geq 18 years who received at least 1 dose of CVnCoV and choose to receive an AV are included in this cohort and will be recommended to procure AV as standard of care per their national vaccination program, if not already done. Subjects will be requested to remain in the trial for safety follow-up until the EOT (Day 393 of the original

Clinical Trial Protocol	CV-NCOV-004
CureVac AG	COVID-19 mRNA Vaccine

Phase 2b/3 schedule). Subjects who were individually unblinded and already received an AV before implementation of Protocol version 4.0 will also be included in this cohort.

Cohort B: CVnCoV only (See Table 5 for the Schedule of Trial Assessments and Procedures): Subjects \geq 18 years who received at least 1 dose of CVnCoV and choose to remain in the trial without receiving any AV will continue follow-up until EOT (Day 393 of the original Phase 2b/3 schedule). Subjects who were individually unblinded during the randomized observer-blinded phase and who received CVnCoV but did not receive an AV before implementation of Protocol version 4.0 and do not intend to receive an AV will also be included in this cohort. Subjects who initially intend to complete the trial without receiving an AV and later decide to receive an AV within the open-label phase will be switched to Cohort A.

Placebo subjects do not require further follow-up and will discontinue the trial (see Section 9.1.4.2).

The open-label phase will provide additional safety data, including data from subjects who receive an AV after CVnCoV. COVID-19 cases will continue to be documented, but there will no longer be any inferential efficacy analysis in the open-label phase (only descriptive summary of cases). Subjects will undergo passive surveillance for COVID-19 (see Appendix 6B).

Trial unblinding and transition from the randomized observer-blinded to the open-label phase will be conducted on a country/site level, depending on full Competent Authority and Ethics Committee approval of Protocol version 4.0 per country/site.

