7.3.3.2 Trial Unblinding

Since the efficacy results from the HERALD trial are available and subjects in this trial are currently allowed to receive an AV, all subjects in this trial will be unblinded. Unblinding will be performed by country/site depending on full Competent Authority and Ethics Committee approval of Protocol version 4.0 per country/site.

The CRO will provide the sites with the subject numbers potentially eligible for each cohort. Each subject will be informed by the Investigator of the available results and whether he/she received CVnCoV or placebo in the trial (see Section 9.1.4).

Subjects who received at least 1 dose of CVnCoV will be asked to remain in the trial to allow safety follow-up. Subjects who received placebo will be withdrawn after trial unblinding.

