9.3.2 Safety Assessments for Subjects in the Open-label Phase

- AESIs will be collected until EOT (Day 393 of the original Phase 2b/3 schedule). AESIs to be monitored include pIMDs and AESIs for SARS-CoV-2 vaccines.
- SAEs will be collected until EOT (Day 393 of the original Phase 2b/3 schedule).
- AEs leading to trial discontinuation will be collected until EOT (Day 393 of the original Phase 2b/3 schedule).

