- If the case start day and the unblinding day occur on the same day the case counts for the analysis. (Censoring starts at the day after the unblinding.)

The following details are to be followed regarding censoring the day after receiving the AV:

- Times are not relevant as neither AV time nor case start time are collected.
- If AV date is complete then censoring starts at first day after the AV day.
- If AV date is incomplete (only day missing) then censoring starts after this month.
- If AV date is incomplete (month missing, year available) then censoring starts after this year.
- If AV date is completely missing then no censoring can be made.

As these imputations of incomplete AV dates are not an ideal solution this is only to be considered as a fallback solution in case complete AV dates cannot be retrieved and as an interim workaround for unclean data during study conduct.

All incomplete or missing AV dates need to be queried.

Site level unblinding:

As each of these subjects receives an unblinding date and time that feeds into the analysis data exactly like the individual unblinding date and time, no difference in censoring process needs to be made for these subjects.

If the subject has never received a CVnCoV dose in this study the subject is discontinued after site-level unblinding, so only the related EOT assessments are censored if performed after the day of unblinding. (Provided the subject has not received an AV before unblinding. In that case the above rules for individual unblinding with AV receipt also apply.)

If the subject has received at least 1 dose of CVnCoV in this study the subject is not automatically discontinued and the subject's data is censored as specified above for individually unblinded subjects.

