12.7 Safety Analyses

12.7.1 Adverse Events

Unsolicited AEs, including SAEs, and AESIs and solicited AEs integrated to or recorded on the CRF are coded using MedDRA Version 23.1 or higher, by SOC and PT.

Only TEAEs as defined in Section 10.5.1 are included in AE summaries. In AE listings, all AEs are included.

Solicited AEs occurring on the day of vaccination and the following 7 days are generally included in summaries if not otherwise stated.

Summaries of medically attended AEs only include those AEs that started up to 6 months after the second trial vaccination, see Section 10.5.6 for further details.

Note that for all summaries by SOC and PT, counting is by subject, not event and subjects are only counted once within each SOC and PT. However, if not stated otherwise, all summaries of unsolicited AEs include the number of AEs reported in each category and all events of a subject are then counted.

All AE summary tables are provided overall, by vaccine group, and by age group and vaccine group and are repeated separately in subjects seronegative at baseline and in subjects seropositive at baseline for SARS-CoV-2 N protein antibody levels (see Section 10.6.1).

In general, percentages are based on the number of subjects in the respective analysis set. In summary tables for AEs after the second vaccination, percentages are based on the number of subjects in the respective analysis set who have received the second vaccination.

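### The uncensored end-of-trial safety tables compare crude percentages by arm, although at sites under protocol version 4.0 placebo follow-up can end before CVnCoV follow-up

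*SAP*

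**What the plan says.** SAP 12.7.1.4 announces: "In the EOT analysis the following outputs are repeated without applying any censoring rules due to subject unblinding or AV receipt". The outputs listed are the overall summary of unsolicited AEs and the tables of unsolicited AEs, SAEs, unsolicited AESIs and fatal AEs by SOC and PT, all up to the end-of-trial visit.

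Two general rules in SAP 12.7.1 set their form. On grouping: "All AE summary tables are provided overall, by vaccine group, and by age group and vaccine group". On denominators: "In general, percentages are based on the number of subjects in the respective analysis set". Follow-up time is defined in SAP 10.13 and used only in the efficacy analyses; no safety table is adjusted for exposure.

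Follow-up after site unblinding differs by arm. For placebo, Protocol 7.3.3.2 says: "Subjects who received placebo will be withdrawn after trial unblinding". SAP 10.11 agrees: "If the subject has never received a CVnCoV dose in this study the subject is discontinued after site-level unblinding". Protocol 9.1.4.2 collects SAEs and AESIs from these subjects up to one closing call. CVnCoV subjects who do not take an authorized vaccine and "choose to remain in the trial without receiving any AV will continue follow-up until EOT" (Protocol 5.1.3) stay in, as do those who take one. For both cohorts, Protocol 9.3.2 states: "SAEs will be collected until EOT (Day 393 of the original Phase 2b/3 schedule"), with the same rule for AESIs and for AEs leading to trial discontinuation. Staying requires new written consent (Protocol 6.3, SAP 9.6.7).

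**The concern.** A percentage of subjects with an event by the end of the trial can be compared between arms only if both arms were watched for similar lengths of time. Randomisation ensured that until site unblinding. After it, the protocol itself ends observation in one arm and continues it in the other, while the table keeps the full arm as the denominator in both.

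SAEs, AESIs and fatal SAEs are primary safety endpoints, and the estimand in SAP 9.5 counts SAEs over the year after the last vaccination. A placebo subject withdrawn before Day 393 cannot complete that year. SAP 12.7.7 acknowledges that censoring removes a large amount of data, and Protocol 5.2 reports nearly 80% of subjects individually unblinded by 18 November 2021. The uncensored repeat is therefore a natural place to look for long-term safety by arm, and a difference there could be taken for a vaccine effect.

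**Working it through.** The plan gives no figure for this comparison, so there is nothing to reproduce.

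**Inputs from the documents**
- Planned arm size 18,250 (Protocol 10.1.1), allocation 1:1.
- End of CVnCoV collection: Day 393. End of placebo collection: day *d*, at site unblinding.
- Protocol version 4.0 is dated 25 November 2021 and SAP version 5.0 is dated 10 March 2022. SAP 6.1 says the latter was created before all authorities had approved version 4.0.

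**Assumptions, not in the documents**
- The same constant hazard in both arms, with an annual risk of 1% for SAEs and 0.1% for deaths as examples.
- A share *c* of CVnCoV subjects re-consents (50%, 80% or 100%); the rest stop at day *d*.
- *d* between 224 and 393. A subject randomised on 16 April 2021 had reached Day 224 on 25 November 2021. SAP Table 10 provides for randomisation around that date at one site, but as a programming rule it does not show that anyone was randomised then.

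**Formula**

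P(event by day t) = 1 − exp(−λt). For rare events the ratio of percentages, CVnCoV to placebo, is close to the ratio of observation times:

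ratio ≈ [c × 393 + (1 − c) × d] / d

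Example, d = 302: c = 1 gives 393/302 = 1.30; c = 0.5 gives (196.5 + 151)/302 = 347.5/302 = 1.15.

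Values from the exponential formula at 1% annual risk (using 0.1% or 2% changes them by less than 0.01):

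| Placebo stops at day d | c = 100% | c = 80% | c = 50% |
|---|---|---|---|
| 224 | 1.75 | 1.60 | 1.38 |
| 260 | 1.51 | 1.41 | 1.25 |
| 302 | 1.30 | 1.24 | 1.15 |
| 330 | 1.19 | 1.15 | 1.09 |
| 360 | 1.09 | 1.07 | 1.05 |
| 393 | 1.00 | 1.00 | 1.00 |

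**In subjects.** With d = 302, c = 100% and 18,250 per arm, λ = −ln(0.99)/365.25 per day. Then P(393) = 1.0756% and P(302) = 0.8275%, or 196 against 151 subjects with an SAE: 45 more on CVnCoV with no true difference. At 0.1% annual risk of death the same case gives about 20 against 15.

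**Late unblinding.** On 10 March 2022, subjects randomised on 15 January, 15 February, 15 March and 16 April 2021 (illustrative dates) had reached Days 420, 389, 361 and 329. Capping at Day 393, with full re-consent, the ratios are 1.00, 393/389 = 1.01, 393/361 = 1.09 and 393/329 = 1.19; their mean is 4.29/4 = 1.07.

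**Early drop-out.** If half of each arm had already left at about Day 150, the d = 302, c = 100% case falls to (75 + 196.5)/(75 + 151) = 271.5/226 = 1.20.

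**Rows affected.** General unsolicited AEs are collected in Phase 2b only, to Day 57 (Protocol Table 6). Medically attended AEs count up to 180 days after the day following the scheduled second dose (SAP 10.5.6): 29 + 1 + 180 = Day 210. For randomisation on 16 April 2021, Day 210 is 11 November 2021, before version 4.0 existed. These rows are essentially untouched. SAEs, AESIs, fatal events and AEs leading to trial discontinuation, which run to the end of the trial, are exposed.

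**After the fix.** Under the same model, events per person-year give a rate ratio of 1.000 in every scenario. Stopping both arms at site unblinding gives equal time and an expected ratio of 1.00.

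**The case against.** The strongest reply is that the comparison which matters is already protected. The main safety tables are censored in both arms the day after unblinding or receipt of an authorized vaccine (SAP 10.11), SAP 12.7.7 leaves them unchanged, and Protocol 10.3.7 plans no formal safety testing. That stands: the defect lies in a descriptive repeat, and a by-arm table without it exists.

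Second, SAP 12.7.1.4 does not itself name the groups, and its outputs match those of SAP 12.7.7, which are shown in four exposure groups. The by-arm form is therefore an inference, though the natural one: SAP 12.7.1 applies to all AE summary tables, and SAP 12.7.7 calls its tables additional. The four-group reading would not remove the problem. Placebo-only time ends at site unblinding or authorized-vaccine receipt, CVnCoV-only time can run to Day 393, and no person-time is given there either.

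Third, the effect is conditional. It arises only where version 4.0 is approved and only for placebo subjects short of Day 393, and refusal to re-consent reduces it. All of this stands. None of it reverses the direction.

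Fourth, a true difference could offset it. Fatal COVID-19 is reported as an SAE, so a real placebo excess in deaths would work the other way. Non-fatal COVID-19 is generally not recorded as an AE (Protocol 9.3.3), so the offset outside deaths would be small.

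**Conclusion.** The point holds as a limited one. Followed as written, at sites under version 4.0, SAP 12.7.1.4 produces by-arm percentages of SAEs, AESIs, fatal events and discontinuation AEs that are expected to be higher for CVnCoV at equal true rates, only because that arm is observed longer. The expected ratio runs from 1.0 (placebo already at Day 393, or version 4.0 not approved), through about 1.15 to 1.30 (placebo stopped at Day 302), to about 1.38 to 1.75 (stopped at Day 224), for re-consent of 50% to 100%. These figures assume equal constant hazards and no earlier drop-out; equal earlier drop-out in both arms shrinks them.

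A reader might infer that the tables will in fact show more SAEs and deaths on CVnCoV, or that an apparent ratio of 1.2 to 1.4 is the likely result. The documents do not support that. They give no enrolment dates, site-unblinding dates or re-consent share. The date 30 November 2021 in SAP 10.6.1 is when Day 393 serology sampling stopped under an urgent safety measure, not a site-unblinding date. Unblinding in March 2022 would bring the ratio to about 1.07 on the dates used above. Nor do the documents support a claim that the main safety comparison is biased in this way.

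**What to change.** In SAP 12.7.1.4, for the SAE, AESI, fatal-event and discontinuation-AE rows:
- Show person-years and events per 100 person-years by arm beside n (%).
- Make the between-arm comparison only on events and time up to the site-level unblinding date, or Day 393 if earlier, in both arms. Where version 4.0 was not approved, the cut is Day 393.
- Put later CVnCoV events in a separate single-arm column.
- Footnote that the comparison still includes time after individual unblinding or receipt of an authorized vaccine.

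Add person-years to the four-group tables of SAP 12.7.7 as well. Rates alone would correct for length of observation if hazards were constant; the common cut also guards against rates that change over time and against selective re-consent.

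No new data are needed. SAP 10.10 says the site-level date is generated in IWRS. The consolidated date of SAP Table 8 takes the earlier of the individual and site dates, so the site-level date must be kept as its own variable. The cost is one date cut and a few columns, and late CVnCoV events no longer appear in the two-arm comparison.

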12.7.2 Deaths and Serious Adverse Events

Description of analyses of SAEs and fatal AEs are included in Section 12.7.1.3.

12.7.3 Laboratory Data

A urine sample for pregnancy testing is taken from women of childbearing potential on Day 1 prior to trial vaccination to establish eligibility. A urine pregnancy test is also performed before the second trial vaccination on Day 29 to continue to determine eligibility. Urine pregnancy test result data is listed only.

No other standard laboratory tests are performed.

12.7.4 Vital Signs

Vital signs are recorded at each clinic visit (i.e. Day 1, Day 29, Day 43, Day 57, Day 120, Day 211, and Day 393 / EOT). Thereby, phase 2b subjects not included in the IS do not have vital signs collected at day 57 and phase 3 subjects do not have vital signs data collected on day 57 and 120.

Scenario A: Vital signs are not collected at EOT visit.

Body temperature (°C), SBP/DBP (mmHg) and pulse (beats per minute) at baseline and each post-baseline timepoint as well as change from baseline at each post-baseline timepoint are summarized.

Vital Signs data are summarized based on the SAS.

12.7.5 Physical Examinations, ECGs, and Other Observations Related to Safety

General physical examinations are performed at Day 1 and Day 393 / EOT. Symptom-directed examinations are performed Day 29, Day 43, Day 57, Day 120, and Day 211.

Scenario A: Physical examinations are not performed at EOT visit.

Physical examination data is listed only.

12.7.6 Sensitivity Analysis on Safety Outputs

12.7.6.1 Safety Delivery when Phase 2b is 6 Weeks post Second Dose

For the safety delivery when all Phase 2b subjects are 6 weeks post 2nd vaccination all safety outputs are repeated without applying any censoring due to subject unblinding.

12.7.7 Adapting the Safety Analyses to the Requirements of Extensive Unblinding

If not explicitly exempted, all safety analyses described in Sections 12.7.1 – 12.7.6 are performed under the conditions of data censoring (described in Section 10.11).

In order to maximally maintain the previous analysis setup while nevertheless aiming at optimally evaluating the collected data the following approach is introduced regarding safety analyses.

1. The above-mentioned analyses (Sections 12.7.1 – 12.7.6) remain unchanged, regardless of extensive individual or site-level unblinding or subjects rolling-over to the OL phase. All definitions still correctly apply and analyses are conducted as originally planned and described above.
2. Additional outputs are planned to account for the massive loss of data due to censoring.
 - a. These additional outputs are closely following the above mentioned safety analyses.
 - b. As far as possible, endpoint definitions and analysis sets are maintained as described in Sections 12.7.1 – 12.7.6.
 - c. No censoring due to unblinding and/or AV receipt is performed.
 - d. AEs/vital sign values are divided into 4 groups: Placebo-only, CVnCoV-only, CVnCoV-AV, AV-only.

AEs/vital sign values are allocated to treatment groups as follows:

- **Placebo-only:** Only placebo has been administered before AE start date / vital signs date. No CVnCoV and no AV must have been administered until then.
- **CVnCoV-only:** At least one dose of CVnCoV and no AV has been administered before AE start date / vital signs date. Placebo might have been administered as well.
- **CVnCoV-AV:** At least one dose of CVnCoV and at least one dose of AV has been administered before AE start date / vital signs date. Placebo might have been administered as well.
- **AV-only:** At least one dose of AV and no CVnCoV has been administered before AE start date / vital signs date. Placebo might have been administered as well.

Treatments are considered “as received”, not “as randomized”.

The following analyses are repeated as described above. All repeat analyses are based on the SAS.

- Overall summary of unsolicited AEs occurring through EOT Visit
- Unsolicited AEs, SAEs, unsolicited AESIs and AEs with fatal outcome, by SOC and PT occurring through EOT Visit

The analyses in this section substitute the analyses of the OL safety endpoints.

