9.6.1 Safety Analysis Sets (SAS, SAS 2, SASsol)

- The SAS includes all subjects randomized in phase 2b or 3 who received at least one dose of CVnCoV or placebo
- The SASsol includes all phase 2b subjects of the SAS with at least one diary collection indicating the occurrence or lack of occurrence of solicited AEs. See Section 10.5.2 for further details.
- The SAS 2 includes all phase 2b subjects of the SAS

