9.6.8 Cohorts in the Open-Label Phase

All subjects who rolled over to the open-label phase are allocated to 1 of these 2 cohorts:

- Cohort A: CVnCoV-AV: OL participants who received an AV before EOT.
- Cohort B: CVnCoV only: OL participants who received no AV before EOT.

Some further clarification notes on subjects who continue in the open-label phase:

- OLS subjects who were already individually unblinded during the randomized observer-blinded phase and who received CVnCoV but – according to their concomitant medication data – did not receive an AV before implementation of Protocol version 4.0 and – according to their concomitant medication data – do not receive an AV until EOT are included in cohort B.
- OLS subjects who were already individually unblinded and – according to their concomitant medication data – either received an AV during the OL phase or already any time during the blinded study phase are included in Cohort A.
- OLS subjects who intended to receive an AV but – according to their concomitant medication data – have not received an AV before EOT are in Cohort B, irrespective of their intention recorded on the CRF.
- OLS subjects who initially intended to participate in the open-label phase without receiving an AV but – according to their concomitant medication data – nevertheless receive(d) an AV (within the open-label phase or already during the blinded study phase) are in Cohort A, irrespective of their intention recorded on the CRF.
- OLS subjects who were not individually unblinded but nevertheless received an AV in the blinded phase are included in Cohort A.

Allocation to cohorts is performed retrospectively. This means: At the time of analysis the concomitant medication data of open-label participants is checked for AV receipt. If the subject has an AV application recorded for any timepoint between first study dose and EOT the subject is eligible for Cohort A. All other open-label phase participants are allocated to Cohort B.

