10.2 Trial Day

Throughout this trial, trial days are defined as follows:

- Day 1 is the day of first trial vaccination.
- For days after first trial vaccination, trial day in the blinded study phase is calculated as

$$\text{Trial Day} = \text{Date of day} - \text{Date of first vaccination} + 1.$$

- For days before first trial vaccination, trial day is calculated as

$$\text{Trial Day} = \text{Date of day} - \text{Date of first vaccination}.$$

- Day 1 of the open-label phase (OL-1) and EOT Day of the open-label phase (OL-2):

The protocol defines OL-1 as Trial Day 302 (-3/+21) and OL-2 as Trial Day 393 (-0/+21) for OLS subjects.

Table 5: Replacement by OL-1 and OL-2 Visits for OLS Subjects

Site Unblinding Timepoint	Day 302 Replaced?	Clinical Visit 7/Day 393 Replaced?
By Day 302	By OL-1	By OL-2
After Day 393	No	No
After Day 302 but before Day 393	No	By OL-2

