10.13 Event Dates, Follow-Up Time, Time to Event Calculation and Censoring

Subject's follow-up time and rules for time to event calculations and censoring are dependent on the definition of the endpoint analyzed.

General formulae for the calculation of follow-up time and time to event are provided below. Table 11 further summarizes the definitions and derivations for the dates to be included in the respective formulae based on the endpoint analyzed.

- For each subject, the follow-up time (days) is defined as:

$$\text{Follow Up Time (days)} = \text{End date of Follow Up} - \text{Start date of Follow Up} + 1.$$

- For each event type, the total follow-up time within each vaccine group is calculated as the sum of all single follow-up times in that group. The total follow-up (years) is calculated as

$$\text{Total Follow Up Time (years)} = \frac{\text{Total Follow Up time (days)}}{365.25}$$

- The time to event (days) for both subjects with an event and censored subjects is calculated as follows:

$$\text{Time to Event (days)} = \text{Event/Censoring Date} - \text{Start Date} + 1.$$

Table 11: Event Dates, Censoring and Follow-Up Time Calculation

ENDPOINT SHORT DESCRIPTION	START DATE	EVENT DATE*	CENSORING DATE#	END DATE OF FOLLOW-UP
FIRST EPISODES OF COVID-19 CASES⁺	2 nd vac. + 15 days	Date of symptoms onset	Min (unblinding date + 1; date AV + 1; trial termination date; cut- off date [^])	Min (Event date; Censoring date; 18-Jun-2021 [§])
FIRST EPISODES OF MODERATE TO SEVERE COVID-19 CASES	2 nd vac. + 15 days	Date of symptoms onset	Min (first episode of mild COVID-19 case date; unblinding date + 1; date AV + 1; trial termination date; cut- off date [^])	Min (Event date; Censoring date; 18-Jun-2021)
FIRST EPISODES OF SEVERE COVID-19 CASES	2 nd vac. + 15 days	Date of symptoms onset	Min (first episode of mild or moderate COVID-19 case date; unblinding date + 1; date AV + 1; trial termination date; cut- off date [^])	Min (Event date; Censoring date; 18-Jun-2021)
FIRST EPISODES OF COVID-19 CASES IN SUBJECTS ≥ 61 YEARS OF AGE	2 nd vac. + 15 days	Date of symptoms onset	Min (unblinding date + 1; date AV + 1; trial termination date; cut- off date [^])	Min (Event date; Censoring date; 18-Jun-2021)
BURDEN OF DISEASE SCORES	2 nd vac. + 15 days	Date of symptom onset of corresponding COVID-19 case	Min (unblinding date + 1; date AV + 1; trial termination date; cut- off date [^])	Min (Event date; Censoring date; 18-Jun-2021)

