12.1 Subject Disposition

A summary of enrollment by region (Latin America vs Europe), country and site is provided for all randomized subjects. This summary is repeated on the OL Set.

The number and percentage of subjects who prematurely withdrew from treatment, prematurely withdrew from the trial before entering the OL phase, rolled over to the OL phase, prematurely withdrew from the trial during the OL phase and a breakdown of the corresponding reasons for treatment withdrawal and early trial discontinuation (summarized separately for blinded and OL phase) is provided.

The number and percentage of subjects randomized and treated is presented with the number and percentage of subjects included in each analysis set. Reasons for exclusion from each analysis set is not tabulated, but listed.

The number of subjects whose data is censored due to unblinding and/or AV application are provided for unblinding and/or AV use before dose 2 and after dose 2. The output is provided for the SAS and for all randomized subjects. A separate listing is provided indicating the date a subject was unblinded / received an AV. Subjects who have received an AV without being unblinded are also included in that listing.

The number and percentage of subjects who were not stratified correctly is presented along with the number of subjects who received an incorrect vaccine at first and/or second vaccination. The summary is done for all randomized subjects. These subjects are also listed.

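### SAP 12.7.7 gives no at-risk N for its two AV states and no person-time for any state, so its through-EOT percentages can differ between states at equal event rates

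*SAP*

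**What the plan says.** SAP 12.7.7 adds safety outputs without censoring for unblinding or AV receipt. Its allocation rule is "AEs/vital sign values are divided into 4 groups: Placebo-only, CVnCoV-only, CVnCoV-AV, AV-only", decided by the treatments given before the AE start date or vital-signs date. The repeated outputs are the overall summary of unsolicited AEs, and the SOC/PT tables of unsolicited AEs, SAEs, unsolicited AESIs and fatal AEs, all through the EOT visit and all on the Safety Analysis Set (SAS). The section states that these outputs take the place of the open-label safety endpoint analyses.

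The overall summary being repeated (SAP 12.7.1.3) shows the number and percentage of subjects. On denominators, SAP 12.7.1 says "In general, percentages are based on the number of subjects in the respective analysis set". Its one exception is tables after the second vaccination, which use subjects who received that dose. SAP 9.6.1 defines the set without reference to AV: "The SAS includes all subjects randomized in phase 2b or 3 who received at least one dose of CVnCoV or placebo".

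Three other planned items come close to what is missing:

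- **SAP 12.1:** "The number of subjects whose data is censored due to unblinding and/or AV application are provided", with a listing of unblinding and AV dates.
- **SAP 12.4.2:** concomitant vaccinations are summarised on the SAS as number and percentage of subjects by product, and SAP 12.0 presents summaries by vaccine group.
- **SAP 10.13:** "follow-up time and rules for time to event calculations and censoring are dependent on the definition of the endpoint analyzed". Table 11, which supplies the dates, lists efficacy endpoints only and ends follow-up no later than unblinding, AV receipt or 18-Jun-2021.

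**The concern.** A percentage of subjects with an event can be compared across columns only if each column counts the subjects at risk in it and they are observed for similar lengths of time. Neither is secured here. A subject is in an AV state only from the first AV dose. The time before that dose counts to CVnCoV-only or Placebo-only. Under Protocol version 4.0, placebo subjects leave after site-level unblinding (SAP 8.3 and 10.11), while re-consenting CVnCoV subjects continue to Day 393.

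The general denominator rule, applied as written, would put subjects who never received an AV into the denominator of an AV column. The open-label cohorts do not help, because "Cohort A: CVnCoV-AV: OL participants who received an AV before EOT" is a fixed, per-subject label on the Open-Label Set. In 12.7.7 the same subject's events before the AV belong to CVnCoV-only.

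In the SAP text these are the only planned tables that separate events after an AV, and they stand in for the open-label safety endpoints. A reader setting CVnCoV-AV beside CVnCoV-only could take a difference in observation time for a difference in risk.

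**Working it through.** SAP 12.7.7 states no N, person-time or rate, so there is no figure to reproduce. The check asks what the planned percentages would show if the event rate were identical in the two CVnCoV states.

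**Inputs**

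- AV uptake f = 0.49. Protocol 5.2 gives approximately 49% of all trial subjects at 18 November 2021. Applying it to the CVnCoV arm is an assumption.
- Follow-up of every subject to Day 393, i.e. 392 days from first dose (schedule in Protocol Tables 4 and 5). Complete follow-up is an assumption.
- Event rate of 1 SAE per 100 person-years in both states (assumption).
- First AV dose on Day d, with d from 120 to 250 (assumption).

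**Formulas**

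Risk over t days: R(t) = 1 − exp(−0.01 × t / 365.25). A subject with an AV spends d − 1 days before it and 393 − d days after it.

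- CVnCoV-only, percent of the arm: (1 − f) × R(392) + f × R(d − 1)
- CVnCoV-AV, percent of the arm: f × R(393 − d)
- CVnCoV-AV, percent of state entrants: R(393 − d)

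**Day 120:** R(392) = 1.0675%, R(119) = 0.3253%, R(273) = 0.7446%. CVnCoV-only = 0.51 × 1.0675 + 0.49 × 0.3253 = 0.704%. CVnCoV-AV on the arm N = 0.49 × 0.7446 = 0.365%.

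| AV timing | CVnCoV-only | CVnCoV-AV, arm N | Ratio | CVnCoV-AV, entrants | Ratio |
|---|---|---|---|---|---|
| All on Day 120 | 0.704% | 0.365% | 1.93 | 0.745% | 0.945 |
| All on Day 211 | 0.825% | 0.244% | 3.39 | 0.497% | 1.66 |
| All on Day 250 | 0.877% | 0.191% | 4.58 | 0.391% | 2.245 |
| Even spread, Days 120–250 | 0.791% | 0.278% | 2.84 | 0.568% | 1.39 |

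The CVnCoV-only percentage is the same under either denominator, because every CVnCoV recipient enters that state. With even spread, uptake of 30% and 70% (assumed) gives ratios of 5.27 and 1.69 on the arm N, and 1.58 and 1.18 on entrants.

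**Person-time check (f = 0.49).** Mean days per arm subject in CVnCoV-only and CVnCoV-AV:

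- Day 120: 0.51 × 392 + 0.49 × 119 = 258, and 0.49 × 273 = 134. Rates per 100 person-years: 0.704% / (258/365.25) = 0.995, and 0.365% / (134/365.25) = 0.996.
- Day 250: 322 and 70 days, giving 0.995 and 0.998.

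The contrast disappears once time is in the denominator. Using entrants alone does not remove it.

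**The documents' only post-AV exposure figure.** Protocol 3.1.5 reports 2535.1 person-years after AV in more than 11,200 subjects across CVnCoV trials in September 2021. That is at most 2535.1 / 11,200 = 0.226 years, about 83 days each. With 83 days after AV, 310 before, 393 days in total, 49% uptake and 2 events per 100 person-years, CVnCoV-only is 1.91% against 0.45% of entrants (ratio 4.2) or 0.22% of the arm (ratio 8.6). That cut pools trials and predates the end of this one, so these ratios are not a forecast.

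**Secondary: SAP 12.7.1.4.** These uncensored repeats have a defined denominator; only follow-up by arm can differ. SAP Table 5 allows site unblinding by Day 302, "After Day 302 but before Day 393", or after Day 393. If placebo subjects leave on Day 302 (301 days) and all CVnCoV subjects complete, the follow-up ratio is 392 / 301 = 1.30. If half re-consent and complete while the rest also stop on Day 302, it is (0.5 × 392 + 0.5 × 301) / 301 = 1.15. If placebo subjects leave on Day 393 or later, it is 1.00.

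**The case against.** A reader might infer that 12.7.7 has no usable denominators at all. The documents do not support that. Every SAS subject received CVnCoV or placebo, so entrants to CVnCoV-only and Placebo-only are the as-treated arm sizes, apart from rare mixed-dose subjects. The denominator rule in 12.7.1 is a default, and its post-dose-2 exception shows that the SAP uses an at-risk denominator where it sees the need. SAP 12.4.2 gives AV recipients by product, and SAP 12.1 lists AV dates. The gap in N is therefore confined to the two AV states.

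That gap remains. The exception does not extend to AV states. Product counts do not give an any-AV total, and counts of censored subjects mix AV receipt with unblinding (nearly 80% unblinded against about 49% with an AV). The TFL list named in SAP Appendix 4 is held outside the SAP and was not available, so it may set the AV column Ns. Column Ns alone would not supply person-time.

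It is also fair to say that safety has no formal testing (Protocol 10.3.7), that no contrast between states is pre-specified, that the blinded-phase safety estimands are counts and percentages and the open-label ones specify no rate, and that any crude percentage depends on follow-up. This limits the consequence. It does not remove the problem, because here unequal time follows from how the states are defined, and the columns sit side by side.

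**Conclusion.** The point holds in this form: for 12.7.7 the SAP text provides no at-risk N for CVnCoV-AV and AV-only and no person-time for any state, and its crude percentages can differ between states when event rates are the same. Under the main illustration the CVnCoV-only to CVnCoV-AV ratio is about 1.9 to 4.6 with the arm N and about 0.95 to 2.2 with entrants. It rests on a constant rate of 1 per 100 person-years, 49% uptake, AV between Day 120 and Day 250, and complete follow-up. The documents fix none of these for the CVnCoV arm.

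A reader might go further and conclude that post-AV risk will be understated. Most scenarios point that way, but the Day 120 entrants case gives 0.945, and the documents settle neither direction nor size. Nor is the trial's safety comparison compromised. Item 1 of 12.7.7 keeps the censored randomized analyses, and efficacy is untouched. What is affected is the interpretation of descriptive tables that replace the open-label safety endpoint analyses. For 12.7.1.4 the issue is minor and may be nil (follow-up ratio 1.00 to 1.30 under the assumptions shown).

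**What to change.** In SAP 12.7.7:

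- Use the subjects who entered each state as the column N. For the AV states, these are subjects with an AV recorded while in follow-up.
- Report person-time per state, splitting each subject at first trial dose, first AV dose and end of follow-up.
- Beside the counts, show SAEs, AESIs, fatal AEs and AEs leading to trial discontinuation as incidence per 100 person-years with 95% CI. The last is an open-label endpoint (SAP 9.4.1) that appears in the overall summary but not in the 12.7.7 SOC/PT list.
- State that the rates assume a roughly constant hazard and do not correct for self-selection into AV, and that subjects with a fully missing AV date cannot be split.

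Align the column Ns in the Appendix 4 TFL list. As a secondary addition, show person-time by arm in 12.7.1.4.

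The cost is SAP wording, TFL column Ns and modest programming. The unblinding and AV dates are already derived for censoring (SAP 10.10 to 10.13), and partly missing AV dates can follow the fallback rules in SAP 10.11. No new data collection is needed.
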